NCT01798641

PI: [name]

Date: March 19, 2013

Principal Investigator: [name]

Application Number: NA 00042178

Protocol March 19th, 2013

Johns Hopkins Medicine - eForm A

 Use the section headings to write the eForm A, inserting the appropriate material in each. If a section is not applicable, leave heading in and insert N/A.

 When submitting eForm A (new or revised), enter the date submitted to the field at the top of eForm A.

1. Abstract

Normal Pressure Hydrocephalus (NPH) is a treatable cause of dementia, gait apraxia and urinary incontinence that results in significant disability if not identified and treated. The pathogenesis of this disease is poorly understood it may involve ischemia damage caused by impaired cerebral blood flow following compression damage to the periventricular white matter. The shunting of CSF using ventriculoatrial (VA) or ventriculoperitoneal (VP) shunt is a commonly employed treatment of NPH. However, accurate diagnosis and selection of patients with shunt responsive NPH is critical for a favorable outcome following shunt surgery. The standard diagnostic tests for NPH such as clinical and radiological findings have proven to be less accurate than desired, with many patients remaining undiagnosed or untreated while others receive treatment due to a falsepositive diagnosis. The response rates to shunting have been reported to vary between 31% to 89%. Furthermore, long term follow-up studies have shown loss of response to shunt which may be due to the natural history of disease, progression of comorbidities or a short term placebo effect following shunt surgery. The aims of this study are to determine (a) patient improvement in gait and other clinical measures in response to active shunt compared to placebo (non-active shunt) (b) predictors of response to shunt (c) long-term outcomes of patients with shunt (d) pilot assessment of sensitivity and specificity of commonly used scales to evaluate NPH. We propose a randomized double-blind cross-over study with a suboptimally draining/non-functioning shunt arm (equivalent of placebo) and an optimally draining/functioning shunt arm. Patients will be followed for 6 weeks on the first arm and then crossed over to the second arm and followed for an additional 6 weeks for the primary aim. Patients will then be followed for two years. Clinical outcomes include changes in gait, cognition, incontinence and functional independence.

Objectives (include all primary and secondary objectives)
 Primary Outcome:
 Changes in Gait

Outcome Measure:

Gait

Tinetti Tool Timed Up and Go task (TUG) MCV Gait Grade

Principal Investigator: [name]

Application Number: NA_00042178

Cognition

Mini Mental State Examination (MMSE)
Rey Auditory Verbal Learning Test (RAVLT)
Trail Making Test A & B
Writing the Alphabet
Beck Depression Inventory
Stroop test
Pegboard

Urinary

Urinary Incontinence Questionnaire (ICIq-UI)
Overactive Bladder Questionnaire (ICIq-OAB)
Quality-of-Life related to lower urinary tract symptoms (ICIq-LUTSqoI)
Global quality-of-life assessment (AUASSqoI)
Voiding diary

Functional Scales

Barthel Index Modified Rankin Scale SMAF Scale of Functional Autonomy

iNPH Scales

Kudo INPH grading Scale Kiefer Index (Gait/balance, headache and dizziness domains)

Outcome Scales

Black Outcome Scale Marmarou Recovery Scale Post-Shunt Surgery Questionnaire

European NPH scale

Core imaging testing:

Sagittal MPRAGE
Axial T2
Axial FLAIR
Sagittal CISS midline

Sagittal phase contrast through the midline

Principal Investigator: [name]

Application Number: NA_00042178

Axial through plane cardiac gated phase contrast imaging aqueduct DTI 30 directions 1 nex

Comorbidity Index

iNPH Diagnosis Checklist

3. Background

Normal Pressure Hydrocephalus (NPH) is a treatable cause of dementia, gait apraxia and urinary incontinence that results in significant disability if not identified and treated. The pathogenesis of this disease is poorly understood but may involve ischemia caused by impaired cerebral blood flow following strain in fibers of periventricular white matter. The standard diagnostic tests for NPH such as clinical and radiological findings have proven to be less accurate than desired, and many patients may remain undiagnosed and untreated. The symptoms of NPH are necessary but not sufficient to diagnose NPH and recommend shunt surgery. CT and MRI findings are not specific for NPH because they overlap with findings of cerebral atrophy or vascular dementia.

Although a shunt insertion improves NPH symptoms, response rates vary from 31% to 89%. 1-5 The largest published prospective series to date, that of Vanneste et al, enrolled 127 NPH patients and reported a 31% rate of improvement⁶. The Dutch NPH Study enrolled 95 patients with a 1year follow-up and observed a 64% rate of improvement⁵. Numerous other series with patients numbering between 25 and 45 have shown variable response rates ranging between 14% and 89% (most being less than 50%) with follow-up typically one year or less⁴. A recent meta-analysis of all series reported in the literature by Hebb et al. found a combined long-term response rate of 29% to CSF shunting⁴. Our preliminary studies have shown that objective physiological measurements of gait and cognitive assessment can demonstrate improvement after shunt^{3,7-9}. Raftopoulos et al, using a wide battery of tests, described improvement in 67% of 21 patients within a 12-month follow-up period¹⁰. However, Savolainen et al found no significant difference in memory disturbances after shunting¹¹. demonstrated a long term improvement rate of 75% after shunting 132 patients with NPH⁸. Duinkerke et al. reported significant improvement in 6 out of 10 patients (60%) over a 6-12 month follow-up period⁹. Thus, despite a vast body of evidence regarding the efficacy of shunt in Normal Pressure Hydrocephalus the response rates remain inconclusive and vary widely. We believe that this problem of variable response is due to lack of universally accepted identification criteria to select patients for shunt surgery and a strong placebo effect which prevails following placement of shunt. We thus propose a randomized, double blind, placebo controlled crossover study designed to assess improvement in gait, incontinence and cognition and to validate our selection criteria. In addition, the study aims to identify scales/instruments of measurement which are most

[figure not shown]
Principal Investigator: [name]

Application Number: NA 00042178

sensitive and specific to progression or improvement in clinical status of the patient. We will therefore correlate scores on the Comorbidity Index, Kubo INPH Scale, Kiefer's index domains for gait/balance, headache and dizziness, European NPH Scale, INPH Diagnosis Checklist with the Black Outcome Scale, Marmarou Recovery Scale, modified Rankin scale, Barthel index. Furthermore, we would test the hypothesis of association of NPH with congenital hydrocephalus or early childhood changes in brain (long standing overt ventriculomegaly) which may manifest as large heads. We will correlate head circumference at baseline and with outcomes at various time points.

4. Study Procedures

[figure not shown]
a. Study design, including the sequence and timing of study procedures (Distinguish research procedures from those that are part of routine care).

Page 4 of 11

Principal Investigator: [name]

Application Number: NA_00042178

Follow-up at 6, 12, 18, 24 months for long-term response rates

The study is a randomized 2x2 double-blinded cross-over design study with two armscomparing optimally functioning shunts (Optimal drainage) to the placebo treatment wherein there is minimal CSF flow through the shunts (sub-optimal drainage). The state of sub-optimal drainage of shunt will be attained by raising the opening pressure of the shunt valve to maximum which will impede the CSF flow. All patients who are candidates for shunt surgery based upon standard of care practice of CSF drainage trial will enter the study. Only patients who are not at significant risk of falls will be included in the study i.e patients with Tinetti score >18. Furthermore, the neurosurgeon/neurologist will not be blinded to patients shunt valve status. Only the nurse practioner or physiotherapist performing the study evaluation would be blinded. All evaluation data would be made available to neurologist/ neurosurgeon remain informed about treatment failure (Tinetti Gait and evaluation <18).

During the initial phase of the study, participants will be randomized in 1:1 allocation ratio to optimally and sub-optimally draining shunt arms. After completion of six weeks the opening pressures for patients in the optimally draining shunt arm will be raised to minimize CSF flow (crossover to sub-optimally draining arm). Likewise, at 6 weeks patients initially in suboptimal drainage arm will have the opening pressures appropriately reduced so that flow through the shunt is optimal (crossover to optimal drainage shunt arm). X-rays will be performed to confirm shunt valve settings. Since the shunt is only effective during the time it is effectively draining and the carryover effect is minimal (i.e., often lasting for no more than a few days), there will be no washout period between arms. Patients will undergo every third week evaluations regardless of the study arm to evaluate safety as well as efficacy. Patients and the psychometrician, physical therapist and nurse practitioner who assess the outcome measures will be blinded to the shunt status. Only the study neurosurgeon and neurologist will be aware of the shunt status, and will make clinical (safety) decisions after being informed of Tinetti gait and balance scores. The follow-up and evaluation timeline is indicated in the algorithm above. The Neurosurgeon will be notified about the gait and balances score and will make a clinical (safety) decision accordingly. Any patient whose gait deteriorates to Tinetti < 18 or has a fall will be regarded as a treatment failure. Patients who are a treatment failure during the

Principal Investigator: [name]

Application Number: NA 00042178

suboptimal drainage arm will have the opening pressure of the valve adjusted. These patients would then be considered to be crossed over to draining arm if they were in the initial suboptimal drainage arm of the study. If a patient who has already been crossed over from optimally draining shunt to sub-optimally draining shunt arm worsens, s/he will have the shunt pressure turned down and will be followed according to standard of care protocol at 6 monthly intervals. During this time, we will collect data on these follow-up visits as part of the research.

Standard of care procedures: Shunt surgery, Post op evaluations while shunt is in optimal drainage setting, 6, 12 months, 18 months and 24 months post-op visit

Research procedures: Visits during non-draining shunt period

b. Study duration and number of study visits required of research participants.

The study duration and number of visits for each participant will vary depending on the arm of the study the patient enters first (flow chart above).

Non-Draining → Draining Shunt arm

Baseline preoperative visit → Shunt surgery → Sub-optimally draining shunt → first visit within 2 weeks from surgery 6 weeks visit, → cross over to draining Shunt arm at 6 week visit along with x-rays confirmation of the new valve settings → 9 weeks visit → 12 weeks visit Total duration 12 weeks from shunt surgery

Number of total Visits=4

Draining → Non-Draining Shunt arm

Baseline preoperative visit → Shunt surgery → Draining shunt → first visit within 2 weeks from first surgery →, 6 weeks visit, → cross over to non-draining Shunt arm at 6 week visit along with x-rays confirmation of the new valve settings → 9 weeks visit → 12 weeks visit Total duration 12 weeks from shunt surgery

Number of total Visits=4

- c. Blinding, including justification for blinding or not blinding the trial, if applicable.

 Patients and raters will be blinded to treatment status to minimize reporting bias. Neurologist and neurosurgeons will not be blinded for safety reasons.
- d. Justification of why participants will not receive routine care or will have current therapy stopped.

The study is designed to compare efficacy of shunt in comparison to sham/placebo (non draining shunt). Though shunt is standard of care it has not been systematically evaluated in a randomized trial. The length of time that a patient will have a non-draining shunt has been limited to 6 weeks and will be shortened if the patient shows a worsening in gait while on that arm.

e. Justification for inclusion of a placebo or non-treatment group.

The placebo arm is included to take into account any placebo effect. Current standard of care treatment of normal pressure hydrocephalus has not been evaluated in a placebo controlled trial. Current guidelines are based on studies which lack a comparison with placebo and their

Principal Investigator: [name]

Application Number: NA 00042178

outcomes have been highly variable. Thus a placebo control is needed to evaluate efficacy of shunt and to improve our selection criteria for shunt insertion.

f. Definition of treatment failure or participant removal criteria.

Failure: Any participant whose gait deteriorates to Tinetti≤18 will be considered a
treatment failure as this is considered under standard of care to be high risk of fall.
Additionally any patient falling due to inability to balance or poor gait would also be
considered a treatment failure.

Any patient deteriorating to failure level or having a fall attributable to gait impairment will be recorded as a treatment failure for that arm of the study and if on suboptimal drainage arm will be crossed over to optimal drainage level.

Patients who fail would however continue to participate in study and data will be collected at all subsequent follow-up points regardless of the study arm as described above. Furthermore, for concerns of patient safety no patient who fails (Tinetti \leq 18) will subsequently have suboptimal drainage in shunt at anytime^{12,13}.

Response:

Gait

- Tinetti gait and balance scale: Measured with respect to baseline (pre-drainage trial scores)
- 2. TUG: Measured with respect to baseline (pre-drainage trial scores)
- 3. MCV Gait Grade: Measured with respect to baseline (pre-drainage trial scores)

Cognition

- 1. Mini Mental State Examination (MMSE)
- 2. Rey Auditory Verbal Learning Test (RAVLT): Measured with respect to baseline (pre-drainage trial scores)
- 3. Trail Making Test A & B: Measured with respect to baseline (pre-drainage trial scores)
- 4. Writing the Alphabet: Measured with respect to baseline (pre-drainage trial scores)
- 5. Beck Depression Inventory

Principal Investigator: [name]

Application Number: NA 00042178

- 6. Stroop test
- 7. Pegboard

Urinary

- 1. Urinary Incontinence Questionnaire (ICIq-UI): Measured with respect to baseline (predrainage trial scores)
- 2. Overactive Bladder Questionnaire (ICIq-OAB): Measured with respect to baseline (predrainage trial scores)
- 3. Quality-of-Life related to lower urinary tract symptoms (**ICIq-LUTSqol**): Measured with respect to baseline (pre-drainage trial scores)
- 4. Global quality-of-life assessment (**AUASSqol**): Measured with respect to baseline (predrainage trial scores)
- 5. Voiding Diary

Functional Scales

- 1. Barthel Index: measured with respect to baseline (pre-drainage trial scores)
- 2. Modified Rankin Scale
- g. Description of what happens to participants receiving therapy when study ends or if a participant's participation in the study ends prematurely.
- Inclusion/Exclusion Criteria3.1 Inclusion Criteria

 - Age of Patients (between 55 to 85 years old)
 - Clinically suspected iNPH with at least gait impairment.
 - Ventriculomegaly defined by CT or MRI, Evans' index > 0.3

Principal Investigator: [name]

Application Number: NA 00042178

- Clinical improvement after 50 cc lumbar tap test.
- MMSE> 14
- Patients with Tinetti gait and balance score>18
- Kiefer Comorbidity index<5
- Informed consent from patient

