3.2 Exclusion Criteria

- Etiology for hydrocephalus other than idiopathic normal pressure hydrocephalus
- MMSE<14
- Patients who have Tinetti gait and balance scores of <18
- Kiefer Comorbidity index>5
- Patients not capable of providing an informed consent.
- History of intra-cerebral hemorrhage

6. Drugs/ Substances/ Devices

- a. The rationale for choosing the drug and dose or for choosing the device to be used.
 CSF diversion using shunt surgery is the standard of care treatment for the normal pressure hydrocephalus
- Justification and safety information if FDA approved drugs will be administered for non-FDA approved indications or if doses or routes of administration or participant populations are changed.

n/a

- c. Justification and safety information if non-FDA approved drugs without an IND will be administered.
- d. n/a

7. Study Statistics

a. Primary outcome variable.

The primary short term outcome variable will be the Tinetti gait and balance score, the MCV Gait Grade and the gait velocity defined as number of steps per second per 30 feet walk at 6 and 12 weeks after surgery.

The primary long term outcome variable will be the Tinetti gait and balance score, the MCV Gait Grade and the gait velocity defined as number of steps per second per 30 feet walk at 6 and 12 months after surgery.

b. Secondary outcome measures.

Secondary outcome measures include the - cognitive and incontinence measures, the Black Outcome Scale, the Marmarou Recovery Scale, the functional measures of the Barthel index,

Principal Investigator: [name]

Application Number: NA_00042178

SMAF Scale and Rankin Scale, Post-Surgery Questionnaire, Kudo iNPH grading scale, Kiefer Index and European NPH Scale.

Also, outcome measures at earlier time points (i.e., the first visit 2 weeks from surgery - and 6-week follow-up) will be examined as well as the slope of the change in the measures over the follow-up.

c. Statistical plan including sample size justification and interim data analysis.

General analytic method:

For each treatment order group, we will calculate the within patient paired differences of the 6 and 12 week follow-up measures. We will examine the distributions of these summary measures, and if not normally distributed, log transformation will be tried. If near normality cannot be achieved then non-parametric analyses will be used.

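### Aim (d) promises sensitivity and specificity of the NPH scales, but the only method stated for it, correlating scales with one another, estimates neither and is not linked to the on/off contrast

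*Combined protocol and SAP*

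**What the plan says.** - **The aim.** The Abstract (section 1) lists four aims. Aim (d) is a "pilot assessment of sensitivity and specificity of commonly used scales to evaluate NPH".
- **The aim narrowed.** Section 3 (Background) says the study seeks the instruments most "sensitive and specific to progression or improvement in clinical status of the patient". That concerns change in a patient, not diagnosis.
- **The method.** The next sentence of the Background begins "We will therefore correlate scores on the Comorbidity Index, Kubo INPH Scale". It goes on to the Kiefer domains, the European NPH Scale and the iNPH Diagnosis Checklist, and correlates all of these "with the Black Outcome Scale, Marmarou Recovery Scale, modified Rankin scale, Barthel index". It does not say whether scores or changes in scores are meant, or at which visit.
- **The statistics section.** Section 7 does not mention aim (d). Under the general analytic method in 7c, for each treatment order "we will calculate the within patient paired differences of the 6 and 12 week follow-up measures", followed by tests of treatment effect. The secondary outcomes in 7b include the "Kudo iNPH grading scale, Kiefer Index and European NPH Scale", as well as the Black, Marmarou, Barthel, SMAF and Rankin scales.
- **Who is enrolled.** Inclusion requires clinically suspected iNPH and "Clinical improvement after 50 cc lumbar tap test". Exclusion 3.2 removes "Etiology for hydrocephalus other than idiopathic normal pressure hydrocephalus".

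**The concern.** Sensitivity and specificity are proportions of patients classified correctly against a yes/no reference at a chosen cut-off. The text gives aim (d) no reference, cut-off, responder definition or time point, and the one method it states produces a different quantity. This is therefore more than missing detail: the stated method cannot answer the stated aim.

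Correlation is also weak evidence for the narrower target. Patients who differ in severity will produce correlated scores on two scales even if neither scale moves when the valve is opened. A scale could look good under the stated method and still be unresponsive to treatment.

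At stake is one of the four aims. The design holds better information for it, namely a randomised order of draining and non-draining periods with blinded raters, but the plan does not direct that information to aim (d).

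**Working it through.** **1. The plan's own figure.** The only sample size in the document is for the Tinetti comparison (7c): difference 5, SD 5, two-sided alpha 0.05, power 80%, N = 34, raised to 42 for 20% dropout. A two-sample t-test with 17 per sequence gives 80.7% power, so 34 reproduces. 34/0.8 = 42.5, so 42 is within rounding. No precision target is given for aim (d), so 34 is used below only as the number of evaluable patients.

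**2. Does a correlation fix sensitivity and specificity?** Assume two bivariate normal scales with r = 0.6 (an illustrative value) and the reference split at its median. Write p for the probability that both the scale exceeds its cut-off and the reference exceeds its median. Then sensitivity = p/0.5 and specificity = 1 − [P(scale above cut-off) − p]/0.5.

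| Scale cut-off | p | P(scale above) | Sensitivity | Specificity |
|---|---|---|---|---|
| −1 SD | 0.478 | 0.841 | 96% | 27% |
| mean | 0.352 | 0.500 | 70% | 70% |
| +1 SD | 0.137 | 0.159 | 27% | 96% |

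The middle row can be checked by hand: p = 1/4 + arcsin(0.6)/(2π) = 0.352, and 0.352/0.5 = 0.705. One correlation fits all three rows, so it determines neither quantity. The correlation itself would be imprecise. By Fisher's z, atanh(0.6) = 0.693 with standard error 1/√31 = 0.180, giving a 95% CI for r of 0.33 to 0.78 at N = 34.

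**3. What precision would sensitivity and specificity have if kept?** Assume 34 evaluable patients, a responder yes/no reference, and about 80% correct in each group. Intervals are exact (Clopper-Pearson). The 20/14 split is an assumption. The other rows use published response rates quoted in the protocol (31%, 64%, 89%), which are not rates of on/off response in this design.

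| Responders / non-responders | Sensitivity (95% CI) | Specificity (95% CI) |
|---|---|---|
| 20 / 14 | 16/20 (56–94%) | 11/14 (49–95%) |
| 11 / 23 (31%) | 9/11 (48–98%) | 18/23 (56–93%) |
| 22 / 12 (64%) | 18/22 (60–95%) | 10/12 (52–98%) |
| 30 / 4 (89%) | 24/30 (61–92%) | 3/4 (19–99%) |

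**4. What would a responsiveness index give?** Let d be the on/off difference divided by its within-patient SD. A large-sample standard error is √(1/n + d²/(2n)). For illustration take d = 5/5 = 1, reading the protocol's SD as that of the on/off difference, and n = 34. The standard error is √(1/34 + 1/68) = 0.21, and the 95% CI is 1 ± 1.96 × 0.21 = 0.59 to 1.41. No cut-off or responder definition is needed.

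**5. Which scales already have an on/off analysis?** Of the scales named in the Background correlation, the Kudo scale (assumed to be the one spelled Kubo there), Kiefer Index, European NPH, Black, Marmarou, Rankin and Barthel are secondary outcomes in 7b. The Comorbidity Index and the iNPH Diagnosis Checklist are not.

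**The case against.** - **The contrast is already planned.** A reader might infer that the plan ignores the randomised on/off comparison. It does not: 7b and 7c cover most of these scales. What stands is narrower. A treatment-effect test on each scale does not compare scales, and nothing assigns those results to aim (d).
- **Complete paired data cannot be assumed.** A reader might also infer that every patient is measured on every scale in both states, so that all 34 contribute. The visit algorithm is a figure not available here, and the text does not give a schedule scale by scale. Section 4f also bars any patient who fails from later suboptimal drainage, so a patient who fails in the optimal-first order never has an off period.
- **Diagnostic specificity is not a separate flaw.** With only tap-test responders with suspected iNPH enrolled, there is no non-NPH group, so diagnostic specificity cannot be estimated. That bites only on the looser wording of the Abstract. Under the Background's wording, the eligibility criteria are no defect.
- **The correlations are not meaningless.** The Objectives section classes the Black and Marmarou scales as outcome scales, so correlating NPH scales with them is a form of anchor comparison. It is fair as description, but still yields neither promised quantity.
- **Five Tinetti points is not a responder definition.** It is tempting to take it as the protocol's own cut-off. Section 7c gives it as a mean difference for sample size. With an SD also of 5, a true mean of 5 and a roughly normal distribution, about half the patients would fall below it. A gait score is also a doubtful reference for cognitive and urinary scales.
- **It is only a pilot.** That excuses wide intervals, not a method that estimates something else.

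**Conclusion.** The point holds in limited form. As written, aim (d) cannot be answered by its stated method: correlations deliver neither of the two promised quantities, and do not show response to drainage. Most of the data for a better answer would be produced by the secondary analyses, but the plan does not connect them to the aim.

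The consequence is confined to one pilot aim; the primary gait analysis is unaffected. The conclusion that correlation is the wrong quantity rests on definitions. The numerical illustrations rest on assumptions: r = 0.6, 34 evaluable patients, accuracy near 80%, the responder splits shown, and d = 1.

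**What to change.** **Preferred.** Restate aim (d) as responsiveness to drainage, labelled pilot.

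- For each scale measured in both periods, report the period-adjusted optimal-minus-suboptimal within-patient difference divided by its SD, with a 95% CI. Compare scales on this index. Because the same patients supply all scales, a bootstrap over patients gives intervals for differences between scales.
- Name the scales that qualify. Those not measured in both states stay outside the comparison.
- State how patients who fail early and lack one state are handled, and report how many contribute to each scale. The carry-forward rule in 7c is written under the primary outcome; say whether it extends to these scales.
- Keep the correlations as descriptive, and say whether they use scores or changes, and at which visit.

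**If sensitivity and specificity are retained.** Pre-specify the reference, cut-offs and time point, and report both with exact intervals. Label any individual Tinetti threshold as an assumption. Drop any diagnostic reading of the aim.

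**Cost.** A few lines of text and a modest amount of analysis. The responsiveness comparison needs no new patients or visits.

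### The head-circumference analysis answers a question within iNPH, not the stated question of whether NPH is associated with an early-life brain condition

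*Combined protocol and SAP*

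**What the plan says.** The last paragraph of section 3 (Background) announces a test: "we would test the hypothesis of association of NPH with congenital hydrocephalus or early childhood changes in brain". It goes on to describe the early change as "long standing overt ventriculomegaly) which may manifest as large heads". The analysis follows in one sentence: "We will correlate head circumference at baseline and with outcomes at various time points".

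Entry is set out in sections 4a, 3.1 and 3.2. Section 4a draws participants from one source: "All patients who are candidates for shunt surgery based upon standard of care practice of CSF drainage trial will enter the study". The inclusion criteria in 3.1 ask for "Clinically suspected iNPH with at least gait impairment", "Ventriculomegaly defined by CT or MRI, Evans' index > 0.3" and "Clinical improvement after 50 cc lumbar tap test". The exclusion criteria in 3.2 begin with "Etiology for hydrocephalus other than idiopathic normal pressure hydrocephalus".

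Head circumference is not among the measures listed under Objectives, nor among the primary and secondary outcomes in section 7. The statistical plan in section 7 does not mention it. The four aims in the Abstract do not include an aetiological one.

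**The concern.** An association between having NPH and having an early-life condition is a comparison. It needs people with and without NPH, or an outside figure for how common the condition, or a large head, is in people without NPH. The plan describes neither. The stated analysis works only inside a group selected for suspected NPH.

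What is at stake is the conclusion drawn from the result. The text promises a hypothesis test, and section 7 does not say how the correlation is to be interpreted. As written, the plan would allow a within-cohort correlation, present or absent, to be reported as the answer to a question about the origin of NPH.

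**Working it through.** The documents give no sample size, effect size or other figure for this aim, so there is no plan figure to reproduce. The 34 and 42 in section 7 belong to the Tinetti comparison. The check is therefore whether the hypothesis, the entry rules and the analysis fit together.

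**Step 1. What the hypothesis needs.** Cross NPH (yes, no) with the early-life condition (yes, no):

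| | Early condition | No early condition |
|---|---|---|
| NPH | a | b |
| No NPH | c | d |

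The association is measured by, for example, the odds ratio (a × d) / (b × c).

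**Step 2. What the entry rules supply.**
- Sections 4a and 3.1 admit shunt candidates with suspected iNPH, enlarged ventricles and improvement after a tap test. Nobody is enrolled as a person without NPH, so by design c = d = 0. The ratio becomes 0/0, which is undefined at any sample size.
- Section 3.2 removes patients whose hydrocephalus has another recognised cause, so known congenital hydrocephalus is missing from cell a.
- Unrecognised early enlargement can remain in cell a, but the documents give no rule for classifying patients as having it. Head size is the only marker offered. The Evans' index threshold does not help, because it says nothing about when the enlargement began.
- Both randomised groups are shunted patients who differ in valve setting, so randomisation supplies no contrast in NPH status.

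**Step 3. What the analysis estimates.** The sentence on correlation does not name what head circumference is to be correlated with at baseline. On any reading, both variables are measured in the same enrolled patients. The estimand is the relation of head size to severity or to outcome, given suspected iNPH.

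**Step 4. Whether that estimand carries the hypothesis.** Two cases show that it does not.
- Suppose all the patients shared an early-life origin. Head size might still fail to predict gait or shunt response, and the correlation could be near zero although the hypothesis is true.
- Suppose no patient had an early-life origin. Head size could still correlate with outcome through sex or body size, for which no adjustment is stated, and the correlation could be clear although the hypothesis is false.

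**Step 5. What the planned numbers can do for the question that remains.** This is for planning only and does not measure the fault above. With two-sided 0.05 and 80% power, Fisher's z gives r = tanh[(1.96 + 0.842) / √(n − 3)].
- n = 42: 2.802 / √39 = 0.449, so r is about 0.42.
- n = 34: 2.802 / √31 = 0.503, so r is about 0.46.

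**The case against.** The strongest reply is that the hypothesis has two limbs. The second concerns early change that shows as a large head, and the exclusion in 3.2 reaches only causes that have been recognised. A patient with long-standing enlargement that nobody diagnosed can enter as idiopathic. This stands: head size will vary in the cohort, and its relation to severity and outcome can properly be studied. It does not supply a comparison with people who do not have NPH.

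A second reply is that entry is on suspicion, and the Abstract accepts that some patients are treated after a false-positive diagnosis. NPH status may therefore not be constant, and shunt response might serve as a rough marker of true disease. This stands in part, and a reader should not infer that every participant certainly has NPH. But the plan does not identify false positives or use them as a comparator. The Abstract also offers natural history, comorbidity and a short-term placebo effect as explanations for loss of response, so non-response does not mark a patient as free of NPH.

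A third reply is that the same cohort could be compared with outside norms for head size. This is correct, and it means that the entry criteria alone do not rule the question out. What is missing is the reference comparison, which the plan does not contain.

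A fourth reply is that this is a brief passage in the Background. That is accepted and sets the severity.

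**Conclusion.** The stated hypothesis and the stated analysis do not match. Followed as written, the plan cannot say whether NPH is associated with congenital hydrocephalus or early childhood brain change. It can say whether head size tracks severity or shunt response among patients with suspected iNPH. The conclusion rests on the entry criteria as written and on there being no comparator or norm in the text; the flow chart in section 4 could not be read.

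The point is minor. The aim is exploratory and does not touch randomisation, the sample size or the primary gait comparison.

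Three stronger readings are tempting, and the documents do not support them.
- A reader might infer that eligibility makes the hypothesis untestable in this cohort. It does not, because a comparison with norms would bear on it.
- A reader might infer that excluding recognised congenital cases cuts off the largest heads and pulls the correlation towards zero. No entry criterion mentions head size, and the documents give neither a head-size distribution nor a count of such exclusions, so no effect can be claimed.
- A reader might take the detectable correlations of 0.42 and 0.46 as the size of the fault. They would be the same if hypothesis and analysis matched.

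**What to change.** Reword the aim in section 3 as exploratory: *within iNPH, is baseline head circumference, adjusted for sex and height, associated with baseline Evans' index, symptom severity and shunt response?* Remove the claim to test an association of NPH with congenital hydrocephalus. Add head circumference to the measures under Objectives, and add a short entry in section 7 naming the variables, the time points and the adjustment, with results reported as estimates and intervals. The restated question would sit naturally beside the Abstract's aim on predictors of shunt response. Adjustment for sex and height is a reviewer's recommendation, because head size can vary with both; the documents do not discuss it.

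If the aetiological question is to be kept, make it a descriptive comparison of head circumference with sex-specific reference norms. Name the norm in advance, and state with the result that recognised congenital cases were excluded under 3.2.

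The cost is a few lines of protocol text and recording height, with sex if it is not already collected. No extra patients are needed and treatment does not change. The downside is a more modest stated aim.
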